GCS Co., Ltd.	GANA V [®]	Final version 5.0	Confidential
	CIP #21E0787	Date: 27/06/2022	Page 1/6

OVERALL SYNOPSIS OF THE CLINICAL INVESTIGATION # 21E0787

ANSM registration #:	2021-A02451-40				
Clinical investigation plan #:	21E0787				
Title of the clinical investigation:	Clinical study for the safety and effectiveness of use of an injectable medical device GANA $V^{\mbox{\tiny B}}$ for facial aesthetic treatment				
Sponsor:	GCS Co., Ltd. [name]				
Development phase	Post market study Interventional Device used according to Instruction For Use (IFU)				
Objectives:	 The primary objective is to evaluate the effectiveness of Gana V[®] in comparison with Sculptra[®] in the correction of Nasolabial Folds (NLFs) 6 months after treatment initiation. The secondary objectives of the study are: To evaluate the effectiveness of Gana V[®] in comparison with Sculptra[®] in the correction of Nasolabial Folds (NLFs) 1^{1/2}, 3, 9, 12, 18 and 24 months after treatment initiation. To evaluate the effectiveness of Gana V[®] in comparison with Sculptra[®] on the global aesthetic improvement 1^{1/2}, 3, 6, 9, 12, 18 and 24 months after treatment initiation. To evaluate the effectiveness of Gana V[®] in comparison with Sculptra[®] on the global aesthetic improvement 1^{1/2}, 3, 6, 9, 12, 18 and 24 months after treatment initiation. To evaluate the effectiveness of Gana V[®] in comparison with Sculptra[®] in reducing NLFs depth and volume 1^{1/2}, 3, 6, 9, 12, 18 and 24 months after treatment initiation. To evaluate the subject satisfaction with Gana V[®] in comparison with Sculptra[®] 1^{1/2}, 3, 6, 9, 12, 18 and 24 months after treatment initiation. To evaluate the injector satisfaction with Gana V[®] in comparison with Sculptra[®] 1^{1/2}, 3, 6, 9, 12, 18 and 24 months after treatment initiation. To evaluate the injector satisfaction with Gana V[®] in comparison with Sculptra[®] after initial injection and touch-up injection if applicable. To evaluate the safety of Gana V[®] in comparison with Sculptra[®]. 				
Design:	 The study will be: double-blinded, randomized, within-subjects: each subject testing both devices, versus comparator, single centre. 				
Planned Sample Size:	55 subjects randomized.				
Number of investigational study sites:	1 site (France)				

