Comparator: Name / code Classification Composition Galenic form Administration route	Mannitol. Sterile freeze		,
Endpoints:	Mean chang treatment ini	tiation, as assessed by a	baseline to 6 months after in independent blinded live inkles Severity Rating Scale
	- Mean 24 m live in - WSF after inder with WSF - Glob 1 ^{1/2} ,	onths after treatment initiation ndependent evaluator. RS responder rates 1 ^{1/2} , 3, treatment initiation as a bendent evaluator. A respo at least 1-point improver RS. al Aesthetic Improvement S 3, 6, 9, 12, 18 and 24 mor	eline to 1 ^{1/2} , 3, 9, 12, 18 and ion as assessed by a blinded 6, 9, 12, 18 and 24 months ssessed by a blinded live nder is defined as a subject nent from baseline on the Scale (GAIS) responder rates of the after treatment initiation a blinded live independent

GCS Co., Ltd.	GANA V [®] CIP #21E0787	Final version 5.0 Date: 27/06/2022	Confidential Page 4/6

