	if the upper-		culptra [®] will be demonstrated CI of the (M6-D0bef) mean
	For the seco	ondary evaluation criteria:	.
	All the variab to their type For quantitat	oles will be described using (quantitative data or qualitat	adapted statistics according tive data). ired t test will be applied to

GCS Co., Ltd.	GANA V [®] CIP #21E0787		Final version 5.0 Date: 27/06/2022	Confidential Page 5/6
For qualitative data a McNemar's test will be applied t proportion of improvement or satisfaction between the The bilateral approach will be used with a significance				n between the products.
Foreseen study duration:		Clinical inves Clinical inves	tigation beginning: Q1 202 tigation end: Q2 2024 tigation global duration: 28 ubject: 24 months + screer	months

GCS Co I th	idential ge 6/6
-------------	--------------------

FLOW-CHART							1		
Procedure	Visit 1 Screenin g	Visit 2 Day 0	Visit 3 M1 ^{1/2}	Visit 4 M3	Visit 5 M6	Visit 6 M9	Visit 7 M12	Visit 8 M18	Visit 9 M24
Days	D-x	D0	D40 ±2	D90 ±2	D180 ±4	D270 ±4	D365 ±7	D540 ±14	D730 ±14
Informed consent form signature	•								
Medical examination	•								
Medical history and previous and concomitant treatments collection	•								
Checking of the inclusion and exclusion criteria	•								
Pregnancy test		●b							
Confirmation of eligibility		●b							
Randomization		•							
WSRS live assessment by a blinded evaluator	•	●b	●b	•	•	•	•	•	•
Macrophotographs		●b	●b	•	•	•	•	•	•
Fringe projection acquisitions (2 areas)		●b	●b	•	•	•	•	•	•
Injection + anaesthesia (if necessary)		•	Touch up						
GAIS live assessment by a blinded evaluator			●b	•	•	•	•	•	•
GAIS assessment by the subjects			●b	•	•	•	•	•	•
Subjective evaluation questionnaire for subjects			●b	•	•	•	•	•	•
ISR assessor		●a	●b+a	•	•	•	•	•	•
ISR subjects		completed each day during 4 weeks after injection and touch up if applicable at home by the subject							
Subjective evaluation questionnaire for injector		●a	●a						
AE and concomitant treatments and procedures collection	•	•	•	•	•	•	•	•	•
Study end									•

Keys:^b: Before injection; ^a: After injection

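### Do some 43 to 50 secondary between-product tests without visible multiplicity control make a false claim of a product difference likely?

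*Combined protocol and SAP*

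**What the plan says.** In the synopsis, the Objectives row sets secondary comparisons of the two products at repeated visits. WSRS correction is compared at six visits other than the primary one ("in the correction of Nasolabial Folds (NLFs) 1^{1/2}, 3, 9, 12, 18 and 24 months after treatment initiation"). The fringe-projection objective is to compare the products "in reducing NLFs depth and volume 1^{1/2}, 3, 6, 9, 12, 18 and 24 months after treatment initiation". Global aesthetic improvement and subject satisfaction follow the same seven visits. The Endpoints row adds WSRS responder rates at seven visits and injector satisfaction after the initial and touch-up injections. The flow chart also schedules "GAIS assessment by the subjects" at seven visits.

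The Statistical methods row gives the tests in fragments. For quantitative data the readable piece is "ired t test will be applied to", without its object. For categorical data it is "For qualitative data a McNemar's test will be applied t", broken mid-word. The level sentence is "The bilateral approach will be used with a significance", with no number and no ending. The primary criterion is separate: one 6-month comparison decided by the upper limit of a confidence interval.

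**The concern.** The readable text contains many two-sided tests of one product against the other. It names no key secondary endpoint, no order of visits and no adjustment, and it does not label the p-values as nominal. If each test were judged alone at 5%, an isolated significant result at one visit on one scale would be expected by chance even with identical products. The stake would be a false statement that one product is better or worse, made from a single result among several dozen.

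**Working it through.** The plan states no family-wise error rate and no readable level, so there is no figure of its own to reproduce.

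**Count of tests** (Objectives, Endpoints, flow chart)
- WSRS change 6, WSRS responders 7, evaluator GAIS 7, depth 7, volume 7, subject satisfaction 7, injector satisfaction 2: 6+7+7+7+7+7+2 = 43.
- With subject GAIS: 43+7 = 50. The flow chart lists it as an assessment; the readable endpoint text names only the blinded evaluator.
- With injector satisfaction also at the seven visits named in the Objectives: 50+7 = 57. The flow chart shows that questionnaire only at D0 and M1½.

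The count is reasonable, but partly inferred. Because the object of the t-test sentence is lost, visit-by-visit testing of quantitative data is itself a reading.

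**Independent tests.** P(at least one) = 1 − (1−α)^k. The level α is an assumption.

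| α assumed | k = 43 | k = 50 |
|---|---|---|
| 1% | 35.1% | 39.5% |
| 5% | 1 − 0.95^43 = 89.0% | 1 − 0.95^50 = 92.3% |
| 10% | 98.9% | 99.5% |

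The expected number of false positives at 5% is 43 × 0.05 = 2.15 or 50 × 0.05 = 2.5, whatever the correlation, provided every test has true size 5%.

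**Correlated tests.** All tests use the same folds in the same subjects, and WSRS responder status is derived from the score already tested as mean change. Independence is therefore the extreme case. The table simulates two-sided z tests (100,000 runs, α = 5%) with assumed correlations.

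| Within endpoint / between endpoints | k = 43 | k = 50 |
|---|---|---|
| 0.5 / 0.2 | 77% | 81% |
| 0.7 / 0.5 | 54% | 57% |
| 0.9 / 0.5 | 42% | 45% |
| 0.9 / 0.8 | 26% | 27% |

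A single common correlation gives 59% and 62% at 0.5, and 29% and 30% at 0.8. So whether a false positive is more likely than not turns on a quantity the documents do not state.

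**Size of McNemar's test.** Of the 43 tests, 20 are quantitative (6+7+7) and 23 are proportions; with subject GAIS there are 30 proportions. With 55 pairs and an assumed 5% to 30% discordance, the exact version has true size 0.14% to 2.87% at nominal 5%. Expected false positives then fall:
- k = 43: 20 × 0.05 + 23 × 0.0014 = 1.03, up to 20 × 0.05 + 23 × 0.0287 = 1.66.
- k = 50: 1 + 30 × 0.0014 = 1.04, up to 1 + 30 × 0.0287 = 1.86.

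The independent-test probability becomes 65% to 85%. The readable text does not say whether the exact version is used.

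**What the text can show.** The t-test, McNemar and level sentences are all incomplete, at the place where a statement on multiplicity or exploratory status would be expected. Only a synopsis is available. Text lost in extraction does not count as missing from the plan.

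**The case for a change.** The strongest case for the concern does not need 5%. At any level in the table the family-wise rate is many times the per-test level, and even the lowest simulated figure at 5%, 26%, is about five times nominal. The layout also offers some support: the level sentence is the last readable fragment before the study-duration row, and a separate multiplicity paragraph might have left a trace. A sentence in the SAP would cost little.

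The count and the arithmetic stand as conditional statements. The layout argument is weak, because whole stretches of text are lost elsewhere in the same tables. An inflated family-wise rate does harm only if a single secondary result may carry a claim, and nothing readable says it may. The possible remedies also show that this is a trade-off. Holm's procedure within each endpoint would still leave 1 − 0.95^7 = 30% across seven endpoint families, or 1 − 0.95^8 = 34% across eight, if these were independent. A fixed sequence would protect a few results and leave the rest nominal. Reasonable statisticians differ on whether secondary endpoints in a post-market study need either.

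**Conclusion.** The concern does not hold as an error in the plan. Counting 43 to 50 tests is fair, and 89% to 92% is correct for independent tests that each have true size 5%. But the 5% is an assumption, independence is implausible for these data, and a lack of multiplicity wording cannot be established from sentences cut off at that point. Under the assumptions examined, the chance of at least one false positive at 5% runs from about 26% to 92%; at 1% it is at most about 40%. The 6-month primary conclusion is untouched, and no readable passage gives a secondary p-value confirmatory weight. Asking for the level and the status of the secondary tests to be stated plainly is a reasonable preference, but it does not rest on a demonstrated fault.
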